5.7.9. Physical Examination and Neurological Examination

Clinically significant abnormalities found at a physical examination or neurological examination will be reported as AEs and will be included in the analyses of AEs.

Study: 221AD304 Version: 2.0

5.10. Immunogenicity

5.10.1. Background

Definition of baseline value

221AD304 baseline value is defined as the latest immunogenicity data collected prior to the first dose. If no immunogenicity data are collected prior to the first dose, 221AD304 baseline value is missing and will be treated as anti-drug antibody negative for immunogenicity analyses.

Treatment-emergent anti-aducanumab antibody positive responses

Post-baseline positive anti-aducanumab antibody responses are defined as treatment-emergent if (1) a subject is antibody negative at 221AD304 baseline; or (2) a subject is antibody positive at 221AD304 baseline but the post-baseline antibody response is more than 2-fold increase in titer compared to the 221AD304 baseline response.

Persistent and transient positive responses:

Subjects with treatment-emergent positive anti-aducanumab antibody responses will be further classified as transient positive under the following conditions:

- if only a single positive evaluation occurs which is not at the last available time point
- or if more than 1 positive evaluation occurs < 112 days (16 weeks) apart and there is at least 1 negative evaluation that occurs thereafter

Subjects with treatment-emergent positive anti-aducanumab antibody responses will be further classified as persistent positive under the following conditions:

- if more than one consecutive positive evaluation occurs ≥ 112 days (16 weeks) apart
- or if a single positive evaluation occurs at the last available time point with no further negative results available

5.10.2. Immunogenicity Analysis

Immunogenicity population will be used to analyze immunogenicity data. An immunogenicity summary table will be presented showing the number of subjects with anti-aducanumab antibody positive response at any time (including baseline), the number of subjects with treatment-emergent anti-aducanumab antibody positive response at each scheduled test visit, the number of subjects with transient positive response, and the number of subjects with persistent positive response. A listing of immunogenicity data for subjects with anti-aducanumab antibody positive results will also be provided. The immunogenicity summary table will be repeated for the core period.

Visit windows for by visit summaries

For immunogenicity by visit summaries, the analysis visit should be defined using visit windows (see Table 9 below).

Study: 221AD304 **Version:** 2.0

Table 9 Visit Windows for Immunogenicity by Visit Summaries

Analysis visit	Target visit day	Analysis visit window
221AD304 baseline	1	Last value prior to the first dose of aducanumab
Week 24	169	[2, 252]
Week 48	337	[253, 420]
Week 72	505	[421, 609]
Week 102	714	[609, 804]
Week 128	897	[805, 986]
Week 154	1078	>=987

6. Changes from Protocol-Specified Analyses

Table 10 lists the changes from protocol-specified analyses, including all analyses that are added, removed, and modified from those originally outlined in the protocol along with associated rationale/background for each change.

Table 10 Summary of Changes from Protocol-Specified Analyses

Protocol	SAP	Rationale/Background
	Excluded	
16.4.2.2. Clinical Laboratory Results Also, summaries of laboratory values categorized based on common toxicity criteria grade will be created	Excluded	CTCAE toxicity grade analyses are replaced with potential clinically significant (PCS) abnormality analyses.

Study: 221AD304 **Version:** 2.0

7. Summary of Changes from the Previous Version of the SAP

Due to early termination of the study, all displays will be presented by safety analysis groups (0 dose of BIIB037, 0 dose of 10 mg/kg, >0 dose of 10 mg/kg in feeder studies), or safety analysis groups stratified by laboratory

Analysis related to exposure/follow-up adjusted incidence rate, by previous exposure duration groups, and time-to-event analyses (Kaplan-Meier analysis) are excluded.

Table 11 provides details on the changes and reasons for changes from the previous version of the SAP.

Table 11 Changes and Reasons for Changes from the Previous Version of the SAP

SAP Version 1.0	SAP Version 2.0	Rationale/Background
Section 1 Description of objective and endpoints	•	
Section 3.2 Background Characteristics	 Excluding non-STAN mandatory analysis on: Time to treatment discontinuation and study withdraw. Screening failure subjects. Number of subjects by region, country. Number of subjects completed the treatment/study by region and country. Change in AD symptomatic medications. Exposure in the feeder studies period. Baseline clinical stage 	Early termination of the study and abbreviated CSR 221AD304 baseline clinical stage (MCI due to AD, mild dementia, moderate dementia, or severe dementia) - In the opinion of the Investigator and not based on National Institute on Aging - Alzheimer's Association criteria (NIA-AA) [McKhann 2011].
	Modifications: • Add categories "27-39, 40-52, 53-65, and >65" to exposure dose categories.	Modified due to the LTE treatment period was added to the study after SAP 1.0 signoff.

Study: 221AD304 Version: 2.0

SAP Version 1.0	SAP Version 2.0	Rationale/Background
	Add "A listing will be generated for subjects with protocol alternations due to COVID-19, based on the data on the protocol alternations due to COVID-19 collected from the protocol alternation CRF page."	
3.3 Efficacy Analysis	Excluded	Early termination of the study and abbreviated CSR
	Excluded	
3.5 Safety Analysis	AE summary Exclude: 1. Summary of AEs stratified by ARIA-E in feeder study 2. AEs occurred within 2 hours from infusion 3. AEs by 12 weeks intervals from first infusion 4. AE from subjects with treatment-emergent positive anti-BIIB037 antibody AE changes: 6. Add listing of non-treatment emergent AEs. ARIA summary exclude: 7. ARIA analysis by previous exposure duration. ARIA summary changes: 9. ARIA duration will be only based on MRI dates, no matter for symptomatic or asymptomatic ARIA. Laboratory analysis:	Early termination of the study and abbreviated CSR AE and ARIA analyses that being considered not informative are excluded and additional analyses are added.

Study: 221AD304 **Version:** 2.0

SAP Version 1.0	SAP Version 2.0	Rationale/Background	
	10. Exclude Grade analysis based on CTCAE. AESI: 11. Add other significant AE analyses on CNS hemorrhages, hypersensitivity, seizure, and fall.		
	Excluded		
5.7.7 Vital Signs	The clinically relevant abnormalities criteria are updated.	Updated based on Biogen standard analysis table.	

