## 8.3. LTE Inclusion Criteria

To be eligible to participate in the LTE period, participants must meet the following eligibility criteria at Week 102:

- 1. Participant must have completed the Core study period (week 102) and adequately tolerated 10 mg/kg of aducanumab during the Core study period in the opinion of the Investigator.
- 2. The participant will continue to derive clinical benefit from treatment with aducanumab, in the opinion of the Investigator.
- 3. The participant (or the participant's legally authorized representative) has the ability to understand the purpose and risks of the study and provide signed and dated informed consent (or assent) and authorization to use confidential health information in accordance with national and local subject privacy regulations.
- 4. Female participants of childbearing potential and male participants must practice effective contraception during the study and for 24 weeks after their last dose of study treatment.
- 5. Apart from a clinical diagnosis of AD, the participant must be in good health as determined by the Investigator, based on medical history.
- 6. Must have the ability to comply with procedures for protocol-related tests.
- 7. Has one informant/care partner who, in the Investigator's opinion, has frequent and sufficient contact with the participant as to be able to provide accurate information about the participant's cognitive and functional abilities. The informant/care partner must minimally be available by phone to provide information to the Investigator and study staff about the participant and agrees to attend in person clinic visits that require partner input for scale completion. An informant/care partner should be available for the duration of the study, and the use of the same informant/care partner for the duration of the study is encouraged.

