SUVR	standard uptake value ratio
TEAE	treatment-emergent adverse event
ULN	upper limit of normal
US	United States
WHO	World Health Organization

Study: 221AD304 **Version:** 2.0

1. Introduction

Study 221AD304 (EMBARK) is an open-label, single-arm clinical study that is being conducted to assess the long-term safety and efficacy of aducanumab in participants with Alzheimer's disease (AD) who were actively participating in aducanumab clinical studies 221AD103, 221AD205, 221AD301, or 221AD302 (hereafter denoted as "feeder studies") as of 21 March 2019. Participants in an aducanumab clinical study at the time of the announcement of early termination of the feeder studies were eligible to enroll in Study 221AD304.

Biogen initiated early termination of the Phase 3b study 221AD304 on 19 September 2023. At that time, all 221AD304 study participants had completed the core portion of the study, and therefore, the primary objective of assessing safety and tolerability of aducanumab and the core of the study had been met. The decision to complete the study early was not based on any safety or efficacy concerns. Participants were notified that their next scheduled study visit would be their last dosing visit. Per protocol, participants were instructed to return to the site for the end of treatment visit followed by the safety follow-up visit (18 weeks after the last dose).

As there was no available post-trial compassionate access mechanism in France, Biogen allowed French participants to remain on treatment beyond September 2023 as planned and to complete the EMBARK LTE in full. These data from the French participants will be added to the dataset for the LTE. As a result, the decision for early termination of EMBARK did not impact French participants in the study. Following Biogen's 31 January 2024 decision to discontinue commercialization and development of aducanumab, study 221AD304 early termination was also initiated in France and the last dose for France participants occurred no later than 01 May 2024. The study participants in France were required to perform a safety follow-up visit 12 weeks after their last dose. The number of assessments conducted at the End of Treatment (EOT) and safety follow-up/End of Study Visit (EOS) visit were reduced to minimize the burden on site and study participants.

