2.3. Study Conduct Following Announcement of Study Termination

On 19 September 2023, Biogen announced the decision to initiate early termination of the EMBARK study. At that time, all subjects had completed the core treatment period, and over 600 subjects were in LTE treatment period.

The requirement for scheduling the last dose visit and last safety follow-up visit was later updated as described in Table 1. Non-France participants were required to have the last-dose

Study: 221AD304 Version: 2.0

visit prior to 31 October 2023, and the safety follow-up visit 18 weeks after their last dose (+/-5 days) and no later than March 8th, 2024.

As there was no available post-trial compassionate access mechanism in France, French participants were allowed to remain on treatment as planned and complete the EMBARK LTE in full. As a result, the decision for early termination of the EMBARK study did not impact French participants in the study.

Following Biogen's announcement of termination of the aducanumab program, EMBARK study termination activities were initiated in France on 31 January 2024. Participants from France were required to have the last-dose visit prior to 01 May 2024, and the safety follow-up visit 12 weeks after their last dose (+/-5 days) and no later than 24 July 2024.

Table 1 Summary of Updates on Last Dose Visit and Safety Follow-up Visit since the Announcement of Study Termination

	Global ex	cluding France		France
Date of study				
updates	Last dose visit	Follow-up visit	Last dose visit	Follow-up visit
	Prior to	18 weeks after the	Prior to	18 weeks after the last
19Sep2023	19Oct2023	last dose	19Oct2023	dose
			Study continues	
	Prior to	18 weeks after the	as originally	
28Sep2023	31Oct2023	last dose	planned	
				30 days after last dose
		No later than	No later than	and no later than
31Jan2023		31Mar2024	01May2024	01Jun2024
		18 weeks after their		12 weeks (90 days)
		last dose (+/-5 days)		after their last dose (+/-
		and no later than		5 days) and no later
22Feb2024		08Mar2024		than 24Jul2024

Changes to Study Execution Following Announcement of Study Termination

The changes to study execution in France sites involve the following, as described in 221AD304 Protocol Clarification Letter 13Feb2024.

1. End of Treatment (EoT) visit (Section 4.2, Table 3)

In Version 4 of the protocol, Section 4.2 Schedul-	e of Events Table 3 currently includes
timepoints for the	as well as clinical efficacy and
safety assessments.	

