Study: 221AD304 Version: 2.0

Clarification Statement

Due to the discontinuation of the Aducanumab program and the early termination of the study,

[figure not shown]
Also, to reduce participant burden, the clinical efficacy assessments will be removed, leaving only safety assessments.

2. Follow-up/End of Study (FU/EOS) Visit: assessments and timing (Section 4.2, Table 3)

Version 4 of the current protocol mandates that participants return for a Follow-up/End of Study visit (also referred to as the safety follow-up visit) 18 weeks after the participant's last dose at 152 weeks (see Section 4.2, Table 3, Schedule of Activities).

Clarification Statement

Due to the discontinuation of the Aducanumab program and the early termination of the study, all participants will be asked to complete their Follow-up/End of Study Visit 12 weeks (+/– 5 days) after the participant's last dose of study treatment. In addition, similar to the End of Treatment Visit, the number of assessments that need to be completed is now reduced to lessen participant burden. These assessments are reported below in Table 2. If a participant has had their last dose of study treatment and it has been more than 12 weeks since their last dose and the participant has not had their safety follow-up, then they should complete a safety follow-up within the next 30 days, as defined in Table 2.

Study: 221AD304 Version: 2.0

Table 2 Revised Schedule of Assessments for the End of Treatment and Follow-up Visits

Study Assessments	Week 154/End of Treatment Visit (within 2 weeks of last dose)	Follow up/End of Study Visit (12 weeks after last dose +/- 5 days)
Body Weight	X	
Hematology, Blood Chemistry, and Urinalysis	X	
Alzheimer's Disease Status	No longer being completed	
Physical Examination	X	X
Neurological Examination	X	X
Vital Signs	X	X
12-Lead Paper ECG	X	
ADA	X	
Aducanumab Serum Concentration	X	

Study: 221AD304 Version: 2.0

Study Assessments	Week 154/End of Treatment Visit (within 2 weeks of last dose)	Follow up/End of Study Visit (12 weeks after last dose +/- 5 days)	
C-SSRS	X	X This will now be completed	
Brain MRI		X	
AE Reporting	Monitor and record continuously throughout the study		
Concomitant Therapy and Procedures	Monitor and record continuously throughout the study		
SAE Reporting	Monitor and record continuously throughout the study		

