For subjects who entered LTE: A Completer is a subject who completed all visits as mandated by protocol inclusive of the Week 154 EOT visit and the Week 170 FU. A subject who discontinued treatment early and remains in study in the protocol specific follow schedule, inclusive of Week 154, is also considered as Complete.

6. Visit window for by-visit analysis

For data that are summarized by visit, assessment from all scheduled visits and unscheduled visits will be mapped to an appropriate analysis visit using a windowing scheme as described in each section.

Unless otherwise specified, if there is more than 1 value in the same analysis visit window for a certain parameter for a participant, then the closest record to the target

Study: 221AD304 Version: 2.0

visit day will be used for the by visit analysis. If there are 2 values in the same analysis visit window with the same distance from the target visit day for a certain parameter for a participant, then the record with the later date will be used for the by visit analysis. If there are 2 values on the same day for a certain parameter for a participant, then the record with the later time will be used for the by visit analysis.

- 7. Baseline values is defined as the most recent non-missing measurement collected prior to the first dose in the study or as the last non-missing measurement collected during screening for subjects not dosed.
- 8. Change from 221AD304 baseline will be defined as post-baseline value minus 221AD304 baseline value.
- 9. Percent change from baseline will be defined as post-baseline value minus baseline value then divided by baseline value.

10. Treatment Emergent

An adverse event is regarded as treatment emergent if the event has onset date/time on or after the first dose date/time of study treatment, or was reported prior to the first dose and subsequently worsens in severity after first dose date. Additional criteria to determine treatment emergent are described in Section 5.7.2.1.

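### SAP Tables 7 and 9 have no End-of-Treatment row, so by-visit summaries omit or mislabel the EOT laboratory and ADA samples of LTE participants stopped before Week 152; separately, Day 609 lies in two ADA windows.

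*SAP*

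**What the plan says.** SAP 3.1 item 6 sets the general rule: "assessment from all scheduled visits and unscheduled visits will be mapped to an appropriate analysis visit using a windowing scheme". Where several records compete, distance from the target day decides; the rule opens with "if there is more than 1 value in the same analysis visit window for a certain parameter for a participant, then the closest record". It gives no rule for one record that fits two windows.

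Table 7 (laboratory) has Week 52 [2, 539], Week 102 [540, 896] and Week 154 from Day 897. Table 9 (ADA) has Week 24 [2, 252], Week 48 [253, 420], Week 72 [421, 609], Week 102 [609, 804], Week 128 [805, 986] and Week 154 from Day 987. SAP 5.10.2 introduces Table 9 with "For immunogenicity by visit summaries, the analysis visit should be defined using visit windows (see Table 9 below".

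On early termination, the SAP Introduction says: "Participants were notified that their next scheduled study visit would be their last dosing visit". An EOT visit then followed. SAP 2.3 says that "over 600 subjects were in LTE treatment period" at the announcement. The revised schedule in SAP Table 2 has a column headed "Week 154/End of Treatment Visit (within 2 weeks of last dose"), with laboratory tests and ADA marked.

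In protocol Table 3, the only LTE laboratory draw is at Week 154/EOT; ADA is drawn at Week 128 and Week 154/EOT. Protocol 8.3 makes the Week 102 visit a condition of LTE entry: "Participant must have completed the Core study period (week 102").

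**The concern.** The windows suit a trial in which the last sample falls near Day 1078. This SAP was written after termination, when an earlier last sample was to be expected for many LTE participants. Without an EOT row, such a sample must compete for a scheduled-week row. Either it loses to a sample drawn on schedule and drops out of the display, or it fills a row for a visit that the participant never reached.

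What is at stake is how the LTE by-visit tables read. Participants with short LTE exposure would show no LTE value in the laboratory means and changes, and the Week 154 row would include people whose last dose was months before Week 152. The same applies to the treatment-emergent ADA counts by visit.

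**Working it through.** **Inputs.** Target days and windows: SAP Tables 7 and 9. First LTE dose at Week 104, Day 729, then every 28 days to Week 152, Day 1065: protocol Table 3. Visit tolerance ±5 days: protocol Table 3. Assumptions: EOT 14 days after the last dose; a Week 102 sample, and a Week 128 ADA sample where reached, taken on schedule.

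**Step 1: reproduce the window bounds.** Midpoints of adjacent targets:

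- Table 7: (365+714)/2 = 539.5 and (714+1078)/2 = 896. The bounds 539/540 and 896/897 match, with no overlap.
- Table 9: 253, 421, (505+714)/2 = 609.5, (714+897)/2 = 805.5, (897+1078)/2 = 987.5. The bounds are 252/253, 420/421, **609/609**, 804/805 and 986/987. Only the Week 72/Week 102 boundary shares a day.

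**Step 2: place each EOT sample.** For the k-th LTE dose, EOT day = 729 + 28(k−1) + 14. Week 152 uses the protocol's Day 1078.

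| Last LTE dose (week) | EOT day | Laboratory, Table 7 | ADA, Table 9 |
|---|---|---|---|
| 104, 108, 112 | 743, 771, 799 | Week 102 window, not selected | Week 102 window, not selected |
| 116, 120, 124 | 827, 855, 883 | Week 102 window, not selected | shown as Week 128; 70, 42, 14 days early |
| 128, 132, 136 | 911, 939, 967 | shown as Week 154; 167, 139, 111 days early | Week 128 window, not selected |
| 140, 144, 148 | 995, 1023, 1051 | shown as Week 154; 83, 55, 27 days early | shown as Week 154; 83, 55, 27 days early |
| 152 | 1078 | Week 154, correct | Week 154, correct |

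The closest contests for selection are not close. The Day 743 sample is 743−714 = 29 days from target, and the Day 911 ADA sample is 911−897 = 14 days from target. The competing scheduled sample is at most 5 days away.

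Over the 12 early last-dose weeks, laboratory gives 6 not selected and 6 given a later label; ADA gives 6 and 6.

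**Step 3: sensitivity to EOT timing.** With EOT 1 day after the last dose, laboratory stays at 6 and 6, and ADA becomes 7 and 5 (the Week 140 EOT on Day 982 now loses to Week 128). Protocol Table 3's nominal days give 1078−1065 = 13 days; that moves every EOT one day earlier and changes no assignment.

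**Step 4: Day 609.** It lies 609−505 = 104 days from the Week 72 target and 714−609 = 105 days from the Week 102 target, so the nearest-target rule puts it in Week 72. It precedes the first LTE dose by 729−609 = 120 days. Correcting it changes none of the 13 rows of Step 2.

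**The case against.** The strongest reply is that these are descriptive displays and the windows do what nearest-target windows normally do. Keeping the real Week 102 sample in the Week 102 row is correct. SAP 5.1 plans no statistical testing. Much of this stands, and it rules out several stronger readings.

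- A reader might infer that the Day 609 overlap causes the loss of EOT samples. It does not: it exists only in Table 9, precedes LTE dosing, and can touch only a sample taken on exactly that day.
- A reader might infer that the samples are discarded from the analysis. They are not. Laboratory shift and PCS tables use all values (5.7.5.2), hepatotoxicity uses post-baseline values at any time, and the any-time, transient and persistent ADA counts and the listing of positives do not use the windows.
- A reader might infer that the primary result is at risk. For LTE-dosed participants the core period ends before the first LTE dose (3.3), so LTE EOT samples lie outside the core primary analysis.
- A reader might say the ADA table contradicts itself, because someone positive only on an unselected EOT sample counts as persistent (5.10.1) yet appears in no visit row. Visit counts and participant-level classes are different quantities and need not add up. The display is harder to follow, but not contradictory.

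The two-week EOT limit is stated for the French sites. For other countries 14 days is an assumption, supported by the Week 152 to Week 154 spacing in the protocol.

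What the reply does not answer is the label itself: a row headed Week 154 that contains samples up to 167 days early, and participants treated in the LTE with no LTE value in the laboratory by-visit tables.

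**Conclusion.** The point holds for by-visit laboratory summaries and by-visit treatment-emergent ADA counts in the LTE. Under the stated assumptions, every EOT sample after a last dose before Week 152 is either not selected or given the label of a visit not reached.

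The number of participants affected cannot be computed. The only size given is the more than 600 in the LTE at the announcement; there is no breakdown by last-dose week, and some may have reached Week 152. A reader might try to derive a count from SAP Table 3, where 1675−1180 = 495 Phase 3 feeder participants could not yet have completed Week 78 by 15 August 2022. That needs a distribution of start dates and an LTE entry rate, and neither is given. Assuming uniform starts is not supported either. Between the March and August 2022 cutoffs, 1180−420 = 760 participants reached the Week 78 opportunity in 153 days, about 5.0 a day. The remaining 495 started over about 182 days, about 2.7 a day.

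The Day 609 overlap is a separate, small boundary error with no bearing on the LTE. Both points are worth correcting because the remedy is cheap; neither threatens the trial's conclusions on core safety.

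**What to change.** 1. Add an End of treatment row (EOT visit or last on-treatment sample) to Tables 7 and 9, filled whatever the study day and shown separately for the LTE. SAP 3.1 item 4 already derives an LTE end-of-treatment date on which to anchor it.
2. Keep early EOT samples out of the Week 128 and Week 154 rows unless they fall within a stated distance of the target. The distance is the sponsor's choice; the documents do not fix one.
3. Make the Table 9 windows disjoint, for example [421, 609] and [610, 804] by the nearest-target rule. Following the table's other lower bounds, which round the midpoint down, would give [421, 608] and [609, 804]. Either works if stated.

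The cost is SAP wording and one row per table, with no new data. The downsides are a smaller N in the Week 128 and Week 154 rows and mixed exposure lengths in the EOT row; giving the range of study days beside that row would make the mixture visible.
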